### 3.6.3 Adverse Events

#### 3.6.3.1 Definitions by Period

AEs will be classified as pre-treatment, treatment-emergent AEs (TEAEs) during the MTX Run-In Period, TEAEs during the Pegloticase + MTX period, or Follow-up AEs. The AE's will be classified as follows:

- Pre-treatment: Onset date prior to the first dose of MTX.
- TEAE during the MTX Run-in Period: Onset date on or after the first dose of MTX until the first pegloticase infusion.
- For subjects who do not receive pegloticase, also include AEs with onset date within 30 days after the last dose of MTX.
- TEAE during the Pegloticase + MTX Period: Onset date on or after the start of the first pegloticase infusion through 30 days after the last dose of pegloticase and/or MTX (whichever is later).
- Follow-up AE: Onset date >30 days after last dose of pegloticase and/or MTX (whichever is later).

#### 3.6.3.2 Overall Summaries

An overall summary of TEAEs for the ITT analysis set will be provided for the MTX Run-in Period, including the number and percentage of subjects with each AE type as well as the number of events for each of the following:

- TEAEs
- Serious TEAEs
- TEAEs related to MTX
- Serious TEAEs related to MTX
- TEAEs with a Rheumatology Common Toxicity Criteria (CTC) of 3 or higher
- TEAEs leading to permanent withdrawal of MTX
- TEAEs related to MTX leading to permanent withdrawal of MTX
- TEAEs leading to death

An overall summary of TEAEs for the safety analysis set will be provided for the Pegloticase + MTX Period, including the number and percentage of subjects with each AE type as well as the number of events for each of the following:

- TEAEs

- Serious TEAEs
- TEAEs related to pegloticase
- TEAEs related to MTX
- Serious TEAEs related to pegloticase
- Serious TEAEs related to MTX
- TEAEs with a Rheumatology CTC of 3 or higher
- TEAEs leading to permanent withdrawal of pegloticase
- TEAEs related to pegloticase leading to permanent withdrawal of pegloticase
- TEAEs leading to permanent withdrawal of MTX
- TEAEs related to methotrexate leading to permanent withdrawal of MTX
- TEAEs leading to death
- TEAEs of special interest

An overall summary of Follow-up AEs for the safety analysis set will be provided, including the number and percentage of subjects with each AE type as well as the number of events for each of the following.

- AEs
- Serious AEs
- AEs with a Rheumatology CTC of 3 or higher
- AEs leading to death

Percentages for the overall summary of AEs during follow-up will be based on the number of subjects in the safety analysis set who had follow-up more than 30 days after last dose of medication.

### 3.6.3.3 Additional Summaries

Additional summaries displaying the number and percentage of subjects experiencing AE's overall and by System Organ Class (SOC) and Preferred Term (PT) will be provided for time periods as shown in the following table. Note that for pre-treatment AE's no summaries will be provided, but these events will be listed.

Additional summaries displaying the number and percentage of subjects experiencing AE's

Summary Overall and by SOC and PT	MTX Run-in Period	Pegloticase + MTX Period	Follow-up Period
TEAEs	X, Y*	Y*	Y
Serious adverse events (SAEs)	X, Y*	Y*	Y
TEAEs by maximum severity	X, Y	Y	Y
TEAEs related to MTX	X, Y*	Y*	Y
TEAEs related to pegloticase		Y*	Y
TEAEs leading to permanent withdrawal of MTX	X, Y*	Y*	
TEAEs leading to permanent withdrawal of pegloticase		Y*	
TEAEs related to MTX by maximum severity	X, Y	Y	Y
TEAEs related to Pegloticase by maximum severity		Y	Y
SAEs leading to permanent withdrawal of MTX	X, Y*	Y*	
SAEs leading to permanent withdrawal of pegloticase		Y*	
TEAEs of COVID-19 by maximum severity	X, Y	Y	Y

\* = summary includes exposure-adjusted incidence rate (EAIR)

X = ITT set; Y = safety analysis set;

overall and by System Organ Class (SOC) and Preferred Term (PT) will be provided for time periods as shown in the following table. Note that for pre-treatment AE's no summaries will be provided, but these events will be listed.

The exposure-adjusted incidence rate (EAIR) will be calculated based on MTX exposure and pegloticase exposure, and will be provided for the summaries as noted in the table above, as well as the overall summary of TEAEs during the Run-in Period and the Pegloticase + MTX Period. For summaries during the Pegloticase + MTX period, the EAIR will be presented for both MTX and pegloticase exposures.

The EAIR is calculated as the total number of subjects with the event divided by the person-years (PY) of exposure for the event. The following formulas will be used for the calculation of PY for each event and treatment in each period:

#### Run-in Period

- For subjects with the event, MTX PY = date of first occurrence of the event – date of first dose of MTX in the Run-in Period + 1.

- For subjects without the event, MTX PY = date of last MTX dose – date of first MTX dose +1 for subjects who do not enter the Pegloticase + MTX Period and PY = Day 1 visit date – date of first dose of MTX in the Run-in Period for subjects who do enter the Pegloticase + MTX Period.

#### Pegloticase + MTX Period

- For subjects with the event, PY (for both MTX and pegloticase exposure) = date of first occurrence of the event – Day 1 visit date + 1.
- For subjects without the event, PY = date of last dose of MTX (for MTX PY) or pegloticase (for pegloticase PY) – Day 1 visit date + 1

The PY will be summed over all subjects exposed to study drug and divided by 365.25 to get the total PY of exposure for each event.

For summaries by SOC, PT, and maximum severity, a subject will only be counted once within an infusion duration group for each SOC based on the maximum intensity level reported for that SOC and once for each unique PT within that SOC level at the maximum intensity level reported for that PT. Similar logic will be applied for summaries by SOC, PT, and relatedness.

For summaries by SOC and PT only, a subject will be counted at most once within an infusion duration group at the SOC level and at most once at each unique PT within the SOC level. Summaries presenting the frequency of TEAEs by SOC and PT will be ordered alphabetically by SOC and then, within a SOC, alphabetically by PT.

All AEs will be listed. The listing of all AEs will also include the infusion duration that corresponds to the start date of the adverse event (as described in Treatment Windowing for “As-Treated” Summaries (Section 3.1.6). TEAEs and the period of onset will be identified in each listing. In total, the following sets of AEs will be provided as listings:

- Adverse Events
- AEs leading to withdrawal of MTX
- AEs leading to withdrawal of pegloticase
- AEs with CTC grade of 3 or higher
- AEs of special interest: major adverse cardiovascular events (reported and adjudicated)
- AEs of special interest: symptoms related to infusion reaction or anaphylactic reactions (reported and adjudicated)
- AEs of special interest: gout flares
- AEs occurring >30 days after last pegloticase infusion
- Serious AEs
- AEs for subjects who died

- AEs for subjects with suspected or confirmed COVID-19

Severity of AE's will be determined using the Rheumatology Common Toxicity Criteria v2.0.

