Investigators will be permitted to adjust the duration of the infusion at a particular infusion visit regardless of initial treatment duration assignment, if needed. The decision to modify the infusion duration at a visit, will be allowed based on the investigator's discretion, after a discussion with the Medical Monitor.

Subjects may return to the original infusion duration for subsequent infusions at investigator's discretion.

Pegloticase will be administered after all pre-dose study visit assessments have been completed at each visit. The date and time of infusion start and stop will be recorded.

During the Pegloticase + MTX Period, subjects will be instructed to take MTX weekly on the same day each week, within 1 to 3 days prior to each pegloticase infusion and one additional weekly dose after the last infusion for subjects who have not stopped pegloticase due to sUA Discontinuation Criteria; however, if a subject does not do so, MTX must be taken  $\geq 60$  minutes prior to each pegloticase infusion.

After Day 1, if a subject becomes unable to tolerate 15 mg of MTX, the MTX dose may be reduced and/or discontinued and the subject may remain in the study (see [Section 9.5.7.3.2.2](#)).

Samples for measurement of sUA levels, PK analysis of pegloticase, pegloticase immunogenicity and MTX Polyglutamate analysis will be collected at visits indicated in the Schedule of Assessments ([Section 2.1](#)).

Safety assessments, including monitoring and recording of all AEs, whether or not drug-related, measurement of vital signs, physical examinations and monitoring of hematology and blood chemistry, will be performed.

[figure not shown]
The total blood volume to be collected from each subject during this study is approximately 450 mL.

An External Adjudication Committee will be established for this study to adjudicate the AESIs. The External Adjudication Committee will be comprised of external experts with experience in immunology, allergic reactions, rheumatology and/or cardiovascular diseases. Details outlining the responsibilities of the Adjudication Committee will be included in the Adjudication Committee charter. AESIs defined in the protocol (See Section 9.6.1.2.1.5) include IRs, anaphylaxis and cardiovascular events. The AESI of gout flare will not be adjudicated.

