### 1.6 Treatment Periods

- MTX Run-in Period
  - For summaries by study visit, only includes Week -4 and Week -2 study visits

- For assignment of study period to ongoing assessments (e.g. AE or CM), includes all activities from the date and time of first MTX dose to the date and time of the first dose of pegloticase.
- Pegloticase + MTX Period
  - For summaries by study visit, includes all visits starting with Day 1 through Week 24 and/or End of Pegloticase visit
  - For assignment of study period to ongoing assessments (e.g. AE or CM), includes all activities from the date and time of the first dose of pegloticase to the date of the Week 24 and/or End of Pegloticase visit

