### 3.4 Endpoint Analysis

Potential intercurrent events (ICE) like discontinuing from the treatment may occur during the study. Subjects who discontinue from the treatment will be encouraged to stay in the study after and data will be collected through planned study completion. These intercurrent events will be addressed using different strategies in the efficacy and safety analyses as appropriate.

In general, treatment policy strategy will be used to account for the ICEs for defining estimands corresponding to continuous efficacy endpoints. For binary responder endpoints, composite strategy will be used. Safety endpoints will be assessed using a while-on-treatment strategy.

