  - Standardized MedDRA Queries (SMQ): Myocardial infarction (broad), Ischaemic Central Nervous System (CNS) Vascular conditions (narrow); Haemorrhagic central nervous system vascular conditions (narrow), Central nervous system vascular disorders, not specified as haemorrhagic or ischaemic (narrow), Embolic and thrombotic events (arterial, venous, vessel type unspecified and mixed arterial and venous) (narrow), Cardiac failure (broad), shock-associated conditions (narrow), Torsade de pointes/QT prolongation (narrow), Arrhythmia related investigations, signs and symptoms (broad), Cardiomyopathy (broad), Supraventricular tachyarrhythmias (narrow), Ventricular tachyarrhythmias (narrow), Conduction defects (narrow)
  - All PTs under SOC of Cardiac disorders
  - HLT Aneurysm
- For non-fatal myocardial infarction: SMQ Myocardial infarction (broad)
- For non-fatal stroke: SMQ: Ischaemic Central Nervous System (CNS) Vascular conditions (narrow); Haemorrhagic central nervous system vascular conditions (narrow); Central nervous system vascular disorders, not specified as haemorrhagic or ischaemic (narrow)
- Congestive heart failure: SMQ Cardiac failure (broad)

The cardiovascular events identified using the aforementioned criteria and the adjudicated cardiovascular events will be summarized by SOC and PT for the MTX Run-in Period and Pegloticase + MTX Period for the safety analysis set. EAIR of pegloticase and MTX will be summarized for the Pegloticase + MTX Period.

The number and percentage of subjects who experienced a gout flare (recorded in the AE eCRF), and number of gout flares per subject will be summarized for the MTX Run-in Period using the ITT analysis set. Percentages will be based on the number of subjects in the ITT analysis set.

The number and percentage of subjects who experienced a gout flare and number of gout flares per subject during the MTX Run-in Period and the Pegloticase + MTX Period (recorded in the AE eCRF) will be provided for the safety analysis set.

Data for the MTX Run-in Period and Pegloticase + MTX Period will be summarized separately, where applicable.

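### In the Pegloticase + MTX Period, the EAIR counts first events up to 30 days after the last dose but ends event-free person-time at the last dose

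*SAP*

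**What the plan says.** SAP 3.6.3.3 defines the EAIR as the number of subjects with the event divided by the PY of exposure for that event, and in this period "the EAIR will be presented for both MTX and pegloticase exposures". Two rules build the PY:

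- With the event: "PY (for both MTX and pegloticase exposure) = date of first occurrence of the event", minus the Day 1 date, plus 1. There is no cap at the last dose.
- Without the event: "For subjects without the event, PY = date of last dose of MTX (for MTX PY) or pegloticase (for pegloticase PY", again counted from Day 1.

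The rows are TEAE and SAE rows. SAP 3.6.3.1 runs the TEAE window for this period "through 30 days after the last dose of pegloticase and/or MTX (whichever is later".

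Two other places bear on the window. SAP 1.6 assigns AEs to this period only up "to the date of the Week 24 and/or End of Pegloticase visit". SAP 3.4 states: "Safety endpoints will be assessed using a while-on-treatment strategy", but gives no AE window. The SAP does not say which of the three governs the EAIR.

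The cardiovascular summary in SAP 3.6.3.4 uses the same rate: "EAIR of pegloticase and MTX will be summarized for the Pegloticase + MTX Period".

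**The concern.** A first event in the 30-day tail enters the numerator and brings its post-dose days with it. An event-free subject followed just as long contributes none of those days. The rate then matches neither of the two quantities a reader would take it for: events during dosing over dosing time, or events in the TEAE window over time in that window.

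The effect is largest for uncommon events, which include many SAE terms and the cardiovascular events, where almost all person-time comes from event-free subjects. It also depends on how long each subject was treated, which is the feature an exposure-adjusted rate is meant to handle.

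**Working it through.** The documents give no EAIR value, so there is no plan figure to reproduce. The check uses the plan's own calendar.

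**Inputs**

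- Study day = 7 × week + 1. This reproduces the target days in SAP 3.1.5, Table 1: Week 22 = 155, Week 24 = 169.
- Last infusion in a completer: Week 22, Day 155.
- Last MTX dose in a completer: Week 23 (Protocol 2.1, MTX dosing row), Day 162.
- End of the TEAE window: 162 + 30 = Day 192.
- End of the SAP 1.6 period in a completer: Day 169.

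**Two subjects side by side.** A first event on Day 190 adds one event and 190 days. An event-free completer followed as long adds 155 days (pegloticase PY) or 162 days (MTX PY).

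**Ceiling for uncommon events.** Let W be the window in which a first event counts and L the event-free days credited. For rare events, planned rate / window rate is about W/L, whenever in the window the events fall.

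| Window | Pegloticase PY | MTX PY |
|---|---|---|
| SAP 3.6.3.1 (Day 192) | 192/155 = 1.239 | 192/162 = 1.185 |
| SAP 1.6 (Day 169) | 169/155 = 1.090 | 169/162 = 1.043 |

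If the last MTX dose keeps its pre-infusion weekday, for example Day 159, the first row becomes 189/155 = 1.219 and 189/159 = 1.189.

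**More common events.** Assume a constant hazard h that does not change after the last dose, and incidence p in the window, so h = −ln(1 − p)/W. Then planned/window rate = 1/(1 − h(W − L)(1 − p)/p). With W = 192:

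| p | Pegloticase PY | MTX PY |
|---|---|---|
| 5% | 1.231 | 1.180 |
| 20% | 1.208 | 1.162 |
| 50% | 1.154 | 1.121 |
| 90% | 1.052 | 1.042 |

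**Example: 110 completers, assumed 5% incidence, 5.5 expected events.** h = 0.0512933/192 = 0.00026715 per day. Event subjects contribute 110 × (0.05/h − 192 × 0.95), about 523 days in all.

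- Planned, pegloticase PY: (104.5 × 155 + 523)/365.25 = 45.8 PY; 5.5/45.8 = 12.0 per 100 PY.
- Planned, MTX PY: (104.5 × 162 + 523)/365.25 = 47.8 PY; 11.5 per 100 PY.
- TEAE-window rate: (104.5 × 192 + 523)/365.25 = 56.4 PY; 9.8 per 100 PY.
- On-treatment rate: 110 × (1 − exp(−155h)) = 4.46 events over 45.7 PY = 9.8 (pegloticase); 4.66 over 47.7 PY = 9.8 (MTX).

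Now let all 5.5 events fall by Day 155, spread evenly (mean Day 78). On pegloticase PY, planned and on-treatment rates agree: 5.5/[(104.5 × 155 + 5.5 × 78)/365.25] = 12.1. The TEAE-window rate is 5.5/[(104.5 × 192 + 5.5 × 78)/365.25] = 9.8. The gap to the window rate remains; the excess over the on-treatment rate is zero.

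**Early stoppers.** Let the last infusion be on day d. Protocol 9.4.3.1.1 stops MTX when infusions cease, but a stop on serum uric acid is identified from a sample taken within 48 hours before the next planned infusion (9.6.2.1), by which time further weekly MTX may have been taken (9.1). The third column therefore puts the last MTX dose at d + 11 to d + 13. Uncommon-event ratios, pegloticase PY:

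| Last infusion | MTX stops same day, (d + 30)/d | MTX continues, (d + 41)/d to (d + 43)/d |
|---|---|---|
| Week 2 (Day 15) | 3.0 | 3.7–3.9 |
| Week 6 (Day 43) | 1.70 | 1.95–2.00 |
| Week 14 (Day 99) | 1.30 | 1.41–1.43 |
| Week 18 (Day 127) | 1.24 | 1.32–1.34 |
| Week 20 (Day 141) | 1.21 | 1.29–1.30 |

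These exceed the completer's 1.239 except for late stops with both drugs ending together (Week 18, 1.236; Week 20, 1.213). Under SAP 1.6 the early-stopper window cannot be fixed, because of its and/or wording.

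**MTX stopped alone.** Protocol 9.1 says "the MTX dose may be reduced and/or discontinued and the subject may remain in the study". If infusions continue to Week 22, the window ends at 155 + 30 = Day 185 while MTX PY ends at the last MTX dose. With an assumed last MTX dose on Day 57, the ratio is 185/57 = 3.2.

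**The case against.** The best defence is that the SAP asks for PY of exposure, that SAP 3.6.2 measures pegloticase exposure from first to last dosing date, and that SAP 3.4 speaks of a while-on-treatment strategy. On that view the denominator is a deliberate dosing-time convention, and 24% is the distance between two conventions rather than an error.

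Part of this stands. The 24% and 19% are measured against the TEAE-window rate only. A reader might infer that every EAIR is 24% too high; the documents do not support that, because against an on-treatment rate the excess depends wholly on first events after the last dose. But the defence does not rescue the formula. A dosing-time rate would leave out post-dose events and end those subjects' PY at the last dose. SAP 3.6.3.3 does neither.

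A second objection is weight. The rates are descriptive, and SAP 3.1.1 plans no inferential testing. With about 5 events, an exact Poisson 95% interval spans roughly 0.3 to 2.3 times the estimate, far wider than 24%. That stands as a limit on importance. It does not excuse a systematic mismatch that can be removed in programming.

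A reader might also infer that comparisons between infusion-duration cohorts are distorted by a known amount. The documents give no early-stopping rate for any cohort, so that size cannot be derived. Nor are the rows on TEAEs and SAEs leading to withdrawal exempt: an AE that starts after the last infusion given and before the next planned one can still lead to withdrawal, so for early stoppers the mismatch reaches those rows too.

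**Conclusion.** The concern holds. As written, the Pegloticase + MTX Period EAIR mixes a numerator window that runs past the last dose with event-free time that does not.

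Against a TEAE-window rate, completers' rates for uncommon events are up to 24% (pegloticase PY) or 19% (MTX PY) higher, or 9% and 4% if SAP 1.6 governs. At 90% incidence the excess is about 5% and 4%, assuming a constant hazard that is unchanged after the last dose. The ratio is generally larger in early stoppers. Against an on-treatment rate, the excess is nil if no first event follows the last dose.

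Affected outputs are the EAIRs in the TEAE, SAE and relatedness rows, the overall TEAE summary and the cardiovascular summary, with the withdrawal rows affected for early stoppers. Counts, percentages and the primary endpoint, which is a proportion, are untouched.

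In the run-in period the same mismatch reaches only ITT subjects who never receive pegloticase, and its size is uncertain. Protocol 2.1, footnote 25, plans an AE contact 30 days after the last MTX dose for subjects generally, whereas Protocol 9.4.4.3 describes post-MTX contact of screen failures at 30 days only for women of childbearing potential. The asterisk in the SAP 3.6.3.3 table may also attach the run-in EAIR to the safety set alone in those rows.

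**What to change.** State in the SAP which of sections 1.6, 3.4 and 3.6.3.1 governs the EAIR, and use one window for both parts.

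- **Option (a), TEAE-window rate.** End event-free PY at the earlier of last contact and the end of the TEAE window. Cost: if events cluster during dosing, the rate falls below the on-treatment rate, by up to 19% (1 − 155/192) on pegloticase PY or 16% (1 − 162/192) on MTX PY for uncommon events in completers when none follow the last dose. The two drug-specific rates also come to share one denominator.
- **Option (b), on-treatment rate.** Keep PY to the last dose, count only first events up to the last dose of that drug, and treat subjects with later events as event-free with PY ending at that dose. Cost: post-dose TEAEs leave the EAIR but stay in the counts. In the example, 4.5 (pegloticase) or 4.7 (MTX) of 5.5 expected events remain.

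For the four withdrawal rows, keep the event count. End event-free PY at the last dose of the named drug for completers, and for early stoppers at the earlier of last contact and the next planned dose of that drug.

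For the run-in period, apply the same alignment to any ITT EAIR that includes subjects who never receive pegloticase, and say which analysis set the asterisk refers to.

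This is a change to SAP formulas and programs. AEs of treated subjects are already collected to the 3-month visit (Protocol 2.1, footnote 10), so no new data are needed for the Pegloticase + MTX Period.

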### 3.6.3.4 AEs of Special Interest

Incidence of IRs, anaphylaxis, gout flares and Major Adverse Cardiovascular Events (MACE) will be summarized for the safety analysis set by infusion duration group. Separate summaries will be produced for adjudicated events and reported events (only applies to IRs, anaphylaxis and MACE events – gout flares are not adjudicated).

Summaries of IRs and anaphylaxis will group events by 3 categories:

- Anaphylaxis
- Infusion reactions including anaphylaxis
- Infusion reactions excluding anaphylaxis

Both the investigator-reported and adjudicated events and the associated signs and symptoms will be summarized separately by severity, and the time relative to the most recent pegloticase infusion for each category above. Signs and symptoms will also be summarized by SOC and PT.

Time relative to the most recent pegloticase infusion will be categorized as: during infusion,  $\leq 2$  hours after infusion,  $> 2$  hours to 24 hours after infusion, and  $> 24$  hours after infusion. If the time of the infusion reaction or anaphylaxis is missing, the category will be assigned as “Missing”.

Serious events and the associated symptoms will be summarized by SOC and PT for each category.

The number of events per subject per treatment infusion duration group, the number of events and serious events per infusion, and the number of subjects with the first event by infusion number will be summarized as well for each category. IRs (including anaphylaxis) that occur on the same date will be considered one event.

In addition, the number and percentage of subjects with adjudicated IRs, including anaphylaxis, will be summarized by severity of event using the following categories for both anti-PEG and anti-uricase antibodies:

- ADA status at baseline (positive or negative)
- ADA status post-baseline (positive or negative)
  - ADA positive post-baseline: negative at baseline and positive at any post-baseline time point, or positive at baseline and with an increase in titer at post-baseline timepoint
  - ADA negative post-baseline: defined as negative at all time points, or positive at baseline and without post-baseline increases in titer from baseline titer

MACEs are defined as: including non-fatal myocardial infarction, non-fatal stroke, cardiovascular death, and congestive heart failure. The following search algorithm will be used to identify possible MACEs:

- For cardiovascular death: any fatal cases with following terms
  - Standardized MedDRA Queries (SMQ): Myocardial infarction (broad), Ischaemic Central Nervous System (CNS) Vascular conditions (narrow); Haemorrhagic central nervous system vascular conditions (narrow), Central nervous system vascular disorders, not specified as haemorrhagic or ischaemic (narrow), Embolic and thrombotic events (arterial, venous, vessel type unspecified and mixed arterial and venous) (narrow), Cardiac failure (broad), shock-associated conditions (narrow), Torsade de pointes/QT prolongation (narrow), Arrhythmia related investigations, signs and symptoms (broad), Cardiomyopathy (broad), Supraventricular tachyarrhythmias (narrow), Ventricular tachyarrhythmias (narrow), Conduction defects (narrow)
  - All PTs under SOC of Cardiac disorders
  - HLT Aneurysm
- For non-fatal myocardial infarction: SMQ Myocardial infarction (broad)
- For non-fatal stroke: SMQ: Ischaemic Central Nervous System (CNS) Vascular conditions (narrow); Haemorrhagic central nervous system vascular conditions (narrow); Central nervous system vascular disorders, not specified as haemorrhagic or ischaemic (narrow)
- Congestive heart failure: SMQ Cardiac failure (broad)

The cardiovascular events identified using the aforementioned criteria and the adjudicated cardiovascular events will be summarized by SOC and PT for the MTX Run-in Period and Pegloticase + MTX Period for the safety analysis set. EAIR of pegloticase and MTX will be summarized for the Pegloticase + MTX Period.

The number and percentage of subjects who experienced a gout flare (recorded in the AE eCRF), and number of gout flares per subject will be summarized for the MTX Run-in Period using the ITT analysis set. Percentages will be based on the number of subjects in the ITT analysis set.

The number and percentage of subjects who experienced a gout flare and number of gout flares per subject during the MTX Run-in Period and the Pegloticase + MTX Period (recorded in the AE eCRF) will be provided for the safety analysis set.

Data for the MTX Run-in Period and Pegloticase + MTX Period will be summarized separately, where applicable.

